Appendix 4 Management of Neutrophil Count Decreased

Neutrophil count decreased should be managed by adjusting the dose of the study drug or performing additional tests/examinations according to the following instructions.

- 1) Neutrophil count decreased to < 1000/μL
 - (1) Repeat neutrophil count measurement immediately.
 - (2) If repeat testing confirms that neutrophil count is $<1000/\mu L$, immediately interrupt study drug administration and repeat the measurement of neutrophil count (the frequency of additional measurements will be determined by the investigator).
 - (3) When neutrophil count recovers to $> 1500/\mu$ L, restart study drug at 1 lower dose level.
- 2) Recurrence of neutrophil count of $< 1000/\mu L$
 - (1) Repeat neutrophil count measurement immediately.
 - (2) If repeat testing confirms that neutrophil count is $< 1000/\mu L$, immediately interrupt study drug administration and repeat the measurement of neutrophil count (the frequency of additional measurements will be determined by the investigator).
 - (3) When neutrophil count recovered to $> 1500/\mu L$, restart study drug at 2 lower dose level from the dose level at which the "1) Neutrophil count decreased to $< 1000/\mu L$ " occurred.

Dose Adjustment

Dose reduction				Dose before	Dose escalation		
Dose level	Dose level	Dose level	Dose level	dose	Dose	Dose	Dose
-4	-3	-2.	_1	increase/	level	level	level
-4	-3	-2	-1	reduction	+1	+2	+3
Intermention	100 mg	150 mg	100 mg	150 mg			
Interruption	qd	qd	bid	bid	_	_	
	Interruption	100 mg	150 mg	100 mg	150 mg		
		qd	qd	bid	bid		
	_	— Interruption	100 mg	150 mg	100 mg	150 mg	
			qd	qd	bid	bid	
		•	T.,.4	100 mg	150 mg	100 mg	150 mg
_			Interruption	qd	qd	bid	bid

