8.6.2.2 Dose adjustment due to adverse events

The dose of the study drug will be adjusted according to the applicable appendices if the following adverse events or abnormal results of laboratory tests, abnormal findings, and abnormal symptoms associated with adverse events are observed.

- Increases in ALT, AST, or bilirubin (see Appendix 3)
- Neutrophil count decreased (see Appendix 4)
- Onset of diarrhea (see Appendix 5)
- Increase in blood pressure (see Appendix 6)

Additionally, if any other severe or serious adverse events with a potential relationship to the study drug are observed, the dose of the study drug should be adjusted at the discretion of the investigator.

If adverse events or abnormal results of laboratory tests, abnormal findings, and abnormal symptoms associated with adverse events which result in dose reduction of study drug recover, the dose of study drug can be re-escalated by 1 dose level in accordance with Table 8.6.2.2-1 based on the investigator's decision.

If adverse events or abnormal results of laboratory tests, abnormal findings, and abnormal symptoms associated with adverse events which leads to interruption of study drug recover, the study drug is restarted at 1 lower dose level than that before the interruption. After restarting the study drug, the dose of study drug can be re-escalated by 1 dose level in accordance with Table 8.6.2.2-1 based on the investigator's decision. The study drug will be restarted at 100 mg qd when the dose regimen before interruption is 100 mg qd. For "2) Recurrence of neutrophil count of < $1000/\mu$ L" in "Appendix 4 Management of Neutrophil Count Decreased" or "3) Recurrence of Grade 3 or 4 diarrhea" in "Appendix 5 Management of Diarrhea," study drug is restarted at 2 lower dose level after the adverse event or laboratory test abnormality, abnormal finding, or symptom associated with the adverse event is recovered. However, the study drug will be restarted at 100 mg qd when the dose before interruption is 100 mg qd or 150 mg qd. The study drug will be administered in the morning when it is administered once daily.

Table 8.6.2.2-1 Dose Adjustment

	Dose re	duction		Dose before	Γ	ose escalatio	n
Dose level -4	Dose level -3	Dose level -2	Dose level	dose increase/ reduction	Dose level +1	Dose level +2	Dose level +3
Interruptio n	100 mg qd	150 mg qd	100 mg bid	150 mg bid	_	_	_
_	Interruptio n	100 mg qd	150 mg qd	100 mg bid	150 mg bid	_	_

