 - Begin treatment with loperamide and continue treatment until the diarrhea has been resolved.
 - a) Up to 2 mg loperamide initial dose.
 - b) If loose stool persists, the dose of loperamide will be adjusted and administration will be continued.
- (2) When diarrhea improves to \leq Grade 1, restart study drug at 1 lower dose level.

3) Recurrence of Grade 3 or 4 diarrhea

- (1) Study drug administration should be interrupted. Diarrhea should be managed until resolution of symptoms in reference to the following items.
 - Initiate aggressive fluid replacement to treat potential dehydration.
 - Consider stool sample for microbiologic evaluation and antibiotics if subject is neutropenic.
 - Begin treatment with loperamide and continue treatment until the diarrhea has been resolved.
 - a) Up to 2 mg loperamide initial dose.
 - b) If loose stool persists, the dose of loperamide will be adjusted and administration will be continued.
- (2) When diarrhea improves to ≤ Grade 1, restart study drug at 2 lower dose level from that at the onset of "2) Grade 3 or 4 diarrhea."

Dose Adjustment

Dose reduction				Dose before	Dose escalation		
Dose level -4	Dose level -3	Dose level -2	Dose level	dose increase/ reduction	Dose level +1	Dose level +2	Dose level +3
Interruptio n	100 mg qd	150 mg qd	100 mg bid	150 mg bid	_	_	_
	Interruptio n	100 mg qd	150 mg qd	100 mg bid	150 mg bid	_	_
	_	Interruptio n	100 mg qd	150 mg qd	100 mg bid	150 mg bid	_
_	_	_	Interruptio n	$100~\mathrm{mg}$ qd	150 mg qd	100 mg bid	150 mg bid

References:

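### Section 8.6.2.2 and Appendices 4 and 5 do not agree on restart after recurrent neutrophils < 1000/µL or recurrent Grade 3/4 diarrhea

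*Protocol*

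**What the plan says.** Section 8.6.2.2 of the protocol sends the investigator to the appendices: "The dose of the study drug will be adjusted according to the applicable appendices". It then sets its own restart rules.

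- General rule after an interruption: "the study drug is restarted at 1 lower dose level than that before the interruption".
- Lowest step for that rule: "The study drug will be restarted at 100 mg qd when the dose regimen before interruption is 100 mg qd".
- Recurrent neutrophils < 1000/µL or recurrent Grade 3/4 diarrhea, citing Appendix 4 item 2) and Appendix 5 item 3) by title: "study drug is restarted at 2 lower dose level after the adverse event or laboratory test abnormality" has recovered. This sentence does not say from which dose the two levels are counted.
- Lowest step for recurrence: "However, the study drug will be restarted at 100 mg qd when the dose before interruption is 100 mg qd or 150 mg qd".

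Appendix 4, item 2)(3), says to "restart study drug at 2 lower dose level from the dose level at which the" first neutrophil event occurred. Appendix 5, item 3)(2), says to "restart study drug at 2 lower dose level from that at the onset of" the first Grade 3 or 4 episode. Neither appendix states a floor. Each prints the same dose adjustment table as 8.6.2.2, and in that table the entry two levels below 150 mg qd is Interruption.

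The synopsis, under its heading on dosing adjustments, has only the one-level restart. It has neither the recurrence rule nor a floor.

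**The concern.** Two things differ between the main text and the appendices: the dose from which the two levels are counted, and whether there is a lowest step. The appendices fix the reference at the first event and are silent on a floor. Section 8.6.2.2 has an explicit floor, keyed to the dose before interruption, and leaves the reference for the two-level step unstated. No order of precedence is given, and each appendix carries its own instructions and table, so a site could work from it alone.

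At stake is the handling of a subject who has a safety event for the second time. Two sites that both follow the protocol could arrive at different steps for the same history, depending on which page they open. The primary endpoint analysis is not threatened.

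**Working it through.** No sample size, power or error rate is involved. The check applies each text to the protocol's own dose table.

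**Inputs**

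- Dose ladder (Table 8.6.2.2-1, repeated in Appendices 4 and 5), numbered here: 1 = 150 mg bid, 2 = 100 mg bid, 3 = 150 mg qd, 4 = 100 mg qd, 5 = Interruption. This numbering reproduces all four rows of the printed table.
- Path: first event, restart one level lower (held at 100 mg qd if already there, as in 8.6.2.2), then recurrence at the restarted dose. No re-escalation or other adjustment in between.

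**Rules**

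- Appendices: step = first-event step + 2, no floor.
- 8.6.2.2, reading A: step = recurrence step + 2, with 100 mg qd if the recurrence dose is 150 or 100 mg qd.
- 8.6.2.2, reading B: two levels counted from the first-event dose, as in the appendices; floor judged on the dose at recurrence.
- 8.6.2.2, reading C: both the count and the floor judged on the first-event dose.

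Reading A follows from the preceding sentence in 8.6.2.2, which counts from the dose before the interruption. It is an inference, because the two-level sentence does not say so.

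**Results**

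| First event at | Recurrence at | Appendices alone | 8.6.2.2, A | 8.6.2.2, B | 8.6.2.2, C |
|---|---|---|---|---|---|
| 150 mg bid (1) | 100 mg bid (2) | 1 + 2 = 3: 150 mg qd | 2 + 2 = 4: 100 mg qd | 150 mg qd | 150 mg qd |
| 100 mg bid (2) | 150 mg qd (3) | 2 + 2 = 4: 100 mg qd | floor: 100 mg qd | 100 mg qd | 100 mg qd |
| 150 mg qd (3) | 100 mg qd (4) | 3 + 2 = 5: Interruption | floor: 100 mg qd | 100 mg qd | 100 mg qd |
| 100 mg qd (4) | 100 mg qd (4) | 4 + 2 = 6: no table entry | floor: 100 mg qd | 100 mg qd | 100 mg qd |

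- Row 1 differs under reading A only.
- Row 2, the path from the protocol's starting dose, agrees under every reading.
- Row 3 differs under all three readings, because the floor stands in 8.6.2.2 and not in the appendices.
- Row 4 can arise only if the 8.6.2.2 floor was used at the first event. The gap is visible already at that first event: one level below 100 mg qd in the appendix table is 4 + 1 = 5, Interruption, while 8.6.2.2 restarts at 100 mg qd.

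**Can the paths occur?** Section 8.6.2.1 allows escalation to 150 mg bid from Week 4, so row 1 is reachable. Row 3 needs a subject already at 150 mg qd at the first neutrophil or diarrhea event. That can follow a one-level reduction from 100 mg bid for another cause, such as blood pressure under Appendix 6 or a platelet count above 250000/µL under 8.6.2.3.

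**The case against.** The strongest reply is that the texts are meant to be read together. The recurrence sentence in 8.6.2.2 cites the two appendix items by title, and the section opens by deferring to the appendices. On that view the appendices supply the missing reference dose and 8.6.2.2 supplies the floor. The doses that the floor names, 150 and 100 mg qd, are exactly those from which two steps down reaches Interruption or leaves the table. Both appendix items also say to restart; neither says to keep the subject off drug. So a reader might infer an outright contradiction between dose rules, but the documents do not prove one. A coherent joint reading exists, and under it every direct path has a single answer.

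That reply disposes of the 150 mg bid example as a firm conflict. It does not dispose of the floor. The joint reading has to be assembled by the reader, no precedence is stated, and a site that opens only Appendix 4 or 5 finds no floor and a table that ends in Interruption.

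A reader might also infer that the dose-reduction and interruption tables would become inconsistent across sites. The documents do not support this. SAP 5.3 reports each adverse event by the highest action taken. In row 1, moving from 100 mg bid to either 150 or 100 mg qd counts as a dose reduction. In row 3, a restart at 100 mg qd from 100 mg qd counts as an interruption, and so does staying off drug, unless the subject is later withdrawn.

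**Conclusion.** The point holds as a failure of the passages to agree, with one direct recurrence path (150 mg qd, then 100 mg qd) on which the appendix rule and table taken alone lead to a different step from 8.6.2.2 under every reading tried. A similar gap exists for a first event at 100 mg qd. The difference after a first event at 150 mg bid depends on the reading, and the path from 100 mg bid shows no difference.

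Few subjects are likely to be affected, but the number cannot be estimated from the documents. A reader might take the overseas incidences in Table 1.4.1-1 as a guide (R788 group: neutropenia 6% in total and 1% severe; severe diarrhea 1%). Those are incidences of any such event on a mild, moderate and severe scale. The trigger here is a recurrence, defined by a confirmed neutrophil threshold or by CTCAE grade, and no recurrence rate is given.

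The conclusion assumes direct paths without re-escalation, and a site that may apply an appendix without turning back to 8.6.2.2. It takes no view on which dose rule is right.

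**What to change.** Reconcile Section 8.6.2.2, Appendix 4 item 2)(3) and Appendix 5 item 3)(2), so that all three name the same reference dose for the two-level step and the same lowest step. Bring the first-event restart at 100 mg qd into line in the same edit, and check the synopsis, which omits both the recurrence rule and the floor. The sponsor must confirm which reference dose and which lowest step are intended.

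The cost is a wording correction at three places, plus the synopsis check. No analysis in the SAP has to change.

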Appendix 5 Management of Diarrhea

Subjects should be made aware that they may experience diarrhea and instructed to contact the clinical site if they experience diarrhea. If diarrhea is observed, the investigator decide grade of diarrhea according to CTCAE v 5.0 (see the table below) and adjust the dose of study drug or perform additional tests in accordance with the following instructions.

Grade of Diarrhea (CTCAE v 5.0)

Grade	Decision criteria
Grade 1	• Increase of < 4 stools per day over baseline
	Mild increase in ostomy output compared to baseline
Grade 2	Increase of 4 to 6 stools per day over baseline
	Moderate increase in ostomy output compared to baseline
	Limiting instrumental activities of daily living
Grade 3	• Increase of ≥ 7 stools per day over baseline
	Hospitalization indicated
	Severe increase in ostomy output compared to baseline
	Limiting self care activities of daily living
Grade 4	Life-threatening consequences; urgent intervention indicated
Grade 5	• Death

Source:

Quoted from Common Terminology Criteria for Adverse Events v 5.0

National Cancer Institute (https://ctep.cancer.gov/)

1) Grade 1 or 2 diarrhea

- (1) Study drug may be continued. Diarrhea should be managed until resolution of symptom in reference to the following items.
 - Discontinue all laxatives.
 - Subjects should be instructed to drink 8 to 10 glasses of water or clear fluids per day.
 - Subjects should be encouraged to make dietary changes including elimination of dairy products and eating smaller but more frequent meals.
 - Consider stool sample for microbiologic evaluation and antibiotics if subject is neutropenic.
 - Grade 1, consider initiating treatment with loperamide according to the regimen below. Grade 2, initiate treatment with loperamide according to the regimen below.
 - a) Up to 2 mg loperamide initial dose.
 - b) If loose stool persists, the dose of loperamide will be adjusted and administration will be continued.
- (2) Subjects with persistent diarrhea (> 48 hours) should be monitored carefully for dehydration and electrolyte imbalance.
- (3) Manage the recurrence of 1) in the same manner.

2) Grade 3 or 4 diarrhea

- (1) Study drug administration should be interrupted. Diarrhea should be managed until resolution of symptoms in reference to the following items.
 - Initiate aggressive fluid replacement to treat potential dehydration.
 - Consider stool sample for microbiologic evaluation and antibiotics if subject is neutropenic.
 - Begin treatment with loperamide and continue treatment until the diarrhea has been resolved.
 - a) Up to 2 mg loperamide initial dose.
 - b) If loose stool persists, the dose of loperamide will be adjusted and administration will be continued.
- (2) When diarrhea improves to \leq Grade 1, restart study drug at 1 lower dose level.

3) Recurrence of Grade 3 or 4 diarrhea

- (1) Study drug administration should be interrupted. Diarrhea should be managed until resolution of symptoms in reference to the following items.
 - Initiate aggressive fluid replacement to treat potential dehydration.
 - Consider stool sample for microbiologic evaluation and antibiotics if subject is neutropenic.
 - Begin treatment with loperamide and continue treatment until the diarrhea has been resolved.
 - a) Up to 2 mg loperamide initial dose.
 - b) If loose stool persists, the dose of loperamide will be adjusted and administration will be continued.
- (2) When diarrhea improves to ≤ Grade 1, restart study drug at 2 lower dose level from that at the onset of "2) Grade 3 or 4 diarrhea."

Dose Adjustment

Dose reduction				Dose before	Dose escalation		
Dose level -4	Dose level -3	Dose level -2	Dose level	dose increase/ reduction	Dose level +1	Dose level +2	Dose level +3
Interruptio n	100 mg qd	150 mg qd	100 mg bid	150 mg bid	_	_	_
	Interruptio n	100 mg qd	150 mg qd	100 mg bid	150 mg bid	_	_
	_	Interruptio n	100 mg qd	150 mg qd	100 mg bid	150 mg bid	_
_	_	_	Interruptio n	$100~\mathrm{mg}$ qd	150 mg qd	100 mg bid	150 mg bid

References:

Appendix 6 Management of Increased Blood Pressure

Increases in blood pressure have proven to be amenable to treatment, generally without a requirement for study drug interruption. Subjects with elevated blood pressure should receive prompt treatment. Blood pressure for all subjects should be kept systolic blood pressure < 140 mmHg and diastolic blood pressure < 90 mmHg; for subjects with increased cardiovascular risk, diabetes or renal insufficiency consideration should be given to maintaining systolic blood pressure < 130 mmHg and diastolic blood pressure < 80 mmHg.

In previous overseas clinical studies evaluating R788, the following antihypertensive agents have been proven effective in managing blood pressure:

- Calcium channel blockers
- Angiotensin converting enzyme inhibitors
- Angiotensin receptor blockers
- β blockers

If antihypertensive therapy does not control systolic blood pressure < 140 mmHg and diastolic blood pressure < 90 mmHg, the investigator adjust the dose of study drug or perform additional tests in accordance with the following instructions.

- 1) Immediately interrupt the study drug when the subject meets either or both of the following criteria.
 - The subject becomes symptomatic due to blood pressure elevation.
 - The blood pressure cannot be brought under control despite best efforts at blood pressure management.
- 2) If systolic blood pressure ≥ 180 mmHg or diastolic blood pressure ≥ 110 mmHg at any time after the start of study treatment:
 - (1) Study drug administration should be interrupted.
 - (2) Initiate antihypertensive medication or increase the dose of the existing antihypertensive drug, if any.
 - (3) Instruct the subject to visit the study institution within 1 week to measure blood pressure.
 - (4) Increase the dose of the antihypertensive drug until systolic blood pressure is controlled at < 140 mmHg and diastolic blood pressure at < 90 mmHg.
 - (5) Restart study drug at 1 lower dose level when systolic blood pressure < 140 mmHg and diastolic blood pressure < 90 mmHg.
 - (6) If systolic blood pressure ≥ 180 mmHg or diastolic blood pressure ≥ 110 mmHg again despite antihypertensive treatment, interrupt study drug.

- 3) If systolic blood pressure \geq 160 mmHg and < 180 mmHg or diastolic blood pressure \geq 100 mmHg and < 110 mmHg at any visit after the start of the study treatment:
 - (1) Continue study drug at assigned dose level.
 - (2) Initiate antihypertensive medication or increase the dose of the existing antihypertensive drug, if any.
 - (3) Instruct the subject to visit the study institution within 2 weeks to measure blood pressure. If the result of measurement still shows systolic blood pressure ≥ 160 mmHg and < 180 mmHg or diastolic blood pressure ≥ 100 mmHg and ≥ 110 mmHg despite aggressive antihypertensive treatment, interrupt study drug.
 - (4) Increase the dose of the antihypertensive drug until systolic blood pressure is controlled at < 140 mmHg and diastolic blood pressure at < 90 mmHg.
 - (5) Restart study drug at 1 lower dose level when systolic blood pressure is controlled at < 140 mmHg and diastolic blood pressure at < 90 mmHg.
- 4) If systolic blood pressure ≥ 140 mmHg but less than 160 mmHg or diastolic blood pressure ≥ 90 mmHg but less than 100 mmHg at any visit after the start of study treatment:
 - (1) Continue study drug at assigned dose level.
 - (2) Instruct the subject to visit the study institution within 2 weeks to measure blood pressure.
 - (3) If systolic blood pressure remains above \geq 140 mmHg or diastolic blood pressure remains \geq 90 mmHg after 2 weeks, initiate or increase antihypertensive therapy.
 - (4) Instruct the subject to visit the study institution once every 2 weeks to measure blood concentration until systolic blood pressure is controlled at < 140 mmHg and diastolic blood pressure at < 90 mmHg.
 - (5) If systolic blood pressure remains ≥ 140 mmHg or diastolic blood pressure remains ≥ 90 mmHg for more than 8 weeks, despite appropriate antihypertensive therapy, reduce dose of study drug at 1 lower dose level.

Dose Adjustment

Dose reduction				Dose before	Dose escalation		
Dose level -4	Dose level -3	Dose level -2	Dose level	dose increase/ reduction	Dose level +1	Dose level +2	Dose level +3
Interruptio n	100 mg qd	150 mg qd	100 mg bid	150 mg bid	_	_	_
_	Interruptio n	100 mg qd	150 mg qd	100 mg bid	150 mg bid	_	_
_	_	Interruptio n	100 mg qd	150 mg qd	100 mg bid	150 mg bid	_
	_	_	Interruptio n	100 mg qd	150 mg qd	100 mg bid	150 mg bid

References:

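### Protocol Appendix 6 item 3)(3) misprints the diastolic recheck limit, so as printed the 2-week interruption trigger for diastolic 100 to 109 mmHg with systolic below 160 mmHg is lost

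*Protocol*

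**What the plan says.** Protocol Section 8.6.2.2 refers dose adjustment for increased blood pressure to Appendix 6, so the appendix is the operative rule. Its numbered items apply "If antihypertensive therapy does not control systolic blood pressure < 140 mmHg and diastolic blood pressure < 90 mmHg". In outline:

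- **Item 1)** orders immediate interruption if the subject has symptoms from the rise, or if "The blood pressure cannot be brought under control despite best efforts at blood pressure management". It gives no time point.
- **Item 2)** orders interruption at systolic 180 mmHg or more, or "diastolic blood pressure ≥ 110 mmHg at any time after the start of study treatment".
- **Item 3)** is entered at systolic 160 to below 180, or at diastolic at or above "100 mmHg and < 110 mmHg at any visit after the start of the study treatment". Step (1) is "Continue study drug at assigned dose level". Step (2) starts or raises antihypertensive treatment. Step (3) sets a recheck within 2 weeks. The systolic half of its condition is "If the result of measurement still shows systolic blood pressure ≥ 160 mmHg and < 180 mmHg". The diastolic half, which closes the sentence and names the action, is printed as "diastolic blood pressure ≥ 100 mmHg and ≥ 110 mmHg despite aggressive antihypertensive treatment, interrupt study drug". Step (4) keeps raising antihypertensives until control. Step (5) restarts study drug one level lower once control is reached.
- **Item 4)** is entered at systolic 140 to below 160, or diastolic 90 to below 100. Step (5) acts if systolic stays at 140 or more, or if "diastolic blood pressure remains ≥ 90 mmHg for more than 8 weeks, despite appropriate antihypertensive therapy, reduce dose of study drug", the reduction being one dose level.

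**The concern.** Step 3)(3) is meant to ask whether the subject is still in the state that brought them into item 3). The systolic half does so: it repeats its entry range of 160 to below 180. The diastolic half carries two lower limits and no upper limit, so it no longer describes the entry range of 100 to below 110.

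At stake is a fixed safety check. Followed literally, a subject at 150/105 mmHg after 2 weeks of aggressive antihypertensive treatment meets no numeric trigger to stop study drug, and step 3)(1) leaves the dose where it is. Hypertension is an expected effect: Protocol Table 1.4.1-1 gives 28% on R788 against 13% on placebo in the overseas Phase III studies, and Section 10.15.5 lists it as an event of special interest. An interruption threshold for such an effect should not have to be inferred.

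**Working it through.** The plan gives no figure to reproduce here; the check is one of logic. All inputs are the limits in Appendix 6 listed above. Write S for systolic and D for diastolic pressure in mmHg.

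**Step 1. Reduce the printed condition.** (D ≥ 100 and D ≥ 110) is the same as D ≥ 110. Every such reading already satisfies item 2), which is S ≥ 180 or D ≥ 110. The printed diastolic limb therefore adds nothing.

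**Step 2. Compare with the intended condition.**
- Printed 3)(3): (160 ≤ S < 180) or (D ≥ 110).
- With the upper limit restored: (160 ≤ S < 180) or (100 ≤ D < 110). This equals the item 3) entry range at every pair of values.

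**Step 3. Take D from 100 to below 110 at the recheck and vary S.**

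| Systolic | Printed 3)(3) or item 2) | Corrected 3)(3) or item 2) | Step 4)(5), after more than 8 weeks |
|---|---|---|---|
| below 140 | not met | met | arguable: neither pressure is in the item 4) entry range, but the step itself states no upper diastolic limit |
| 140 to 159 | not met | met | applies: item 4) is entered through its systolic limb |
| 160 to 179 | met (systolic limb) | met | not needed |
| 180 or more | met (item 2) | met | not needed |

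The loss is confined to the first two rows. In them, the printed step catches 0 of the 10 whole-number diastolic values from 100 to 109, and the corrected step catches 10 of 10. Section 10.9 bases decisions on the mean of three readings when the first is above 130 systolic or 80 diastolic, so the deciding value need not be whole; the same logic holds for any value from 100 to below 110.

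**Step 4. Timing and strength of the next numeric action.** More than 8 weeks is more than 56 days; the recheck is at most 14 days out. If both clocks start at the first reading in the range (an assumption, since step 4)(5) does not state its start), the gap is more than 56 − 14 = 42 days, or 6 weeks. If the 8 weeks start later, the gap is longer. The action is also weaker: one level down is 300 to 200 mg/day from 150 mg bid, or 200 to 150 mg/day from 100 mg bid. Only from 100 mg qd is the next level down itself an interruption (Table 8.6.2.2-1).

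**Step 5. Does the correction lose anything?** It removes D ≥ 110 from step 3)(3). Item 2) orders interruption for all of those readings, so nothing is lost.

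**The case against.** The best counter-case has three parts.

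**The intent is plain.** The item 3) heading gives the upper limit of 110. The word still in step (3) points back to that range, and a subject who entered at 100 to 109 cannot still be at 110 or more. The systolic half repeats its own range, and step (5) presupposes that interruption can occur within item 3). A careful site would probably read it correctly. This stands, and it is why the point is minor. It does not make the printed threshold right.

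**Item 1) covers much of the gap.** A subject still at 100 to 109 despite aggressive treatment may well count as uncontrolled, with control stated in the lead-in as below 140 and below 90. This also stands: interruption under item 1) is mandatory. What item 1) lacks is a date and a level at which the judgement must be made, which is what step 3)(3) was there to supply.

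**The sign may be an artefact.** The protocol is a translation read from PDF, and the ALT/AST classes in Protocol Section 14.6.5 also have doubtful inequality signs. This cannot be excluded. Against it, the less-than sign is read correctly in the systolic half of the same sentence and in the item 3) heading.

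A reader might go further and infer that subjects with diastolic 100 to 109 have no protection, or that no numeric study-drug action remains for them. The documents do not support either. Item 1) and the antihypertensive steps 3)(2) and 3)(4) still apply. With systolic 140 to 159, step 4)(5) applies without argument. No numeric action remains only if systolic is below 140 and step 4)(5) is also held to its entry range.

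**Conclusion.** Step 3)(3) is wrong as written. Its diastolic condition duplicates item 2), and the numeric interruption trigger at the recheck within 2 weeks is lost for diastolic 100 to below 110 with systolic below 160. What replaces it depends on systolic pressure: a one-level reduction after more than 8 weeks for 140 to 159, and the same reduction only on a broad reading for below 140. Item 1) is a mandatory backstop throughout, without a time point.

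This is a minor correction to a safety rule. The primary endpoint, its test, alpha and the sample size are untouched. The number of subjects affected cannot be derived from the documents, which give no distribution of diastolic pressure. Confidence that the error exists in the Japanese text that sites worked from is only medium, because that text is not available here; nor can it be inferred that any site followed the literal wording.

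**What to change.** First compare step 3)(3) with the Japanese original. Then change the second sign so that the diastolic limb reads ≥ 100 mmHg and < 110 mmHg, matching the item 3) heading. If only the English is wrong, correct the translation alone. If the Japanese carries the same error, correct it and send sites a short clarification. The cost is one symbol and, at most, that note. No visits or procedures are added.
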